This study will not include women in that the specific research questions are targeted toward males. This study will specifically target Latinos. Individuals from other ethnic backgrounds are excluded as the study intervention is specifically tailored to address and target the specific needs and preferences of older Latinos with risk of cardiometabolic disease. This study is specific to only Latino males and will only report data on Latino males; findings from the study are intended to only be generalizable to Latino males. Both Black and White Latino males will be included in the study. We are not powered to detect differences between racial groups of Latino men. Previous research indicates that the outcomes in this study along with engagement with the intervention suggests no differences between racial groups of Latino males; no significant differences have been found in any outcomes in HOLA pilot data. We will use respondent self-report or self-identification to collect data on ethnicity and race. Though this application talks of racial/ethnic disparities and refers to Latino as an ethnicity, we are aware of the limitations of this construct. We acknowledge that ethnicity is a social construct and that Latinos are not a homogeneous, monolithic group even though the U.S. Census definition classifies them into one uniform ethnicity. Also, many racial/ethnic differences that have been identified in previous research are in fact confounded by socioeconomic status (SES). However, even though SES is indeed a central determinant of health status and overlaps with the concept of race, SES does not account for all racial health disparities.

6) **Number of Subjects***

18 older Latinos age 50+ will be enrolled.

7) **Study-Wide Recruitment Methods***

Recruitment procedures will protect participant confidentiality.

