Project Evaluation: we will use a project evaluation questionnaire developed by investigators at the CNSA and used in previous studies. The items are a mix of rating scales, yes/no questions, and open-ended questions that allow participants to give feedback in short answer format with specific interest in understanding the participants' opinions regarding the specific components of the intervention.

After the baseline assessment, participants will be enrolled into the HOLA intervention.

Intervention Description: Content and Structure of HOLA

HOLA is a 16-week multi-component, health promotion intervention for older Latinos with subthreshold depression or anxiety. Aside from the maintenance phase (described below), the length and content of the intervention remain unchanged from the pilot study.

The first component of HOLA consists of two manualized social and physical activation sessions. Prior to beginning the group walk phase, each participant will meet individually with a CHW for the physical and social activation session. This session will last 30 minutes. The purpose of this session is to (a) educate potential participants about the goals of the intervention; (b) to motivate participants to engage in physical activity; (c) to increase participants' social activities (d) identify potential obstacles that may interfere with meeting the demands of the intervention; and (e) to brainstorm ways to overcome these obstacles. Participants will meet individually with the CHW for 30 minutes during week 8 to discuss progress of physical and social activity goals. These meetings will be held in the participants' homes.

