As a pilot study, we will evaluate the feasibility of recruitment, assessment procedures, retention, acceptability, and implementation of HOLA in a sample of midlife and older Latinos living with HIV (**Aim 1**). Consistent with recommendations from biostatistical workgroups funded by NIH, this pilot study is not powered to test a hypothesis. This approach to analysis of feasibility data mirrors the structure of the first HOLA trial and other pilot trials conducted at the CNSA. Successful recruitment will be defined as meeting 100% of targeted sample (N = 18), with 20% or less of eligible subjects refusing to participate. Adequate retention will be defined as 85% or more of randomized subjects completing the post-intervention assessment. Acceptability is defined as 80% or more of sessions attended by subjects. To identify modifications needed in the design of a larger, confirmatory randomized controlled trial (**Aim 2**), we will use a project evaluation questionnaire developed by investigators at the CNSA and used in previous studies. The items are a mix of rating scales, yes/no questions, and open-ended questions that allow participants to give feedback in short answer format with specific interest in understanding the participants' opinions regarding the specific components of the intervention. To explore changes in cardiometabolic risk factors (waist circumference, dyslipidemia, hypertension, and glucose), psychosocial functioning (depression and anxiety severity, social support), and health-related quality of life (**Aim 3**), a one-way ANOVA will be used to illustrate the change in scores from baseline to post-intervention in all the outcome measures used.

A repeated measures ANOVA, as we have proposed, is appropriate to explore the intervention effects on cardiometabolic risk factors,

IRB Study Number: 20181032

Version 8, Date: 07/16/2021

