psychosocial functioning, and health-related quality of life given that this type of analysis is often used in studies that investigate either changes in mean scores over three or more time points. In the exploratory analyses, we will use age, SES, and years of education as covariates. In addition, a list of current medications will also be collected at baseline. Should the participants' medications be dose-adjusted, changed altogether, or if they are started on new medications such as statins, then we will adjust for them in them in the exploratory analysis as well. Covariates will be tested as moderators of treatment response.

Maintenance of Confidentiality:

Our staff is CITI certified and trained with maintenance of confidentiality. The information provided by study participants will be held as personal and confidential to the extent permitted by law. In addition to the safeguards included as part of the recruitment and screening process by assigning a patient a study ID to de-identify participants, all study participants will be given the contact information for the Principal Investigators to answer any questions that may arise. Participants will be informed that they may end their participation at any time without affecting access to any other services they may receive from the UM/JMMC Adult HIV Outpatient Clinic. All study procedures will be conducted according to good clinical practice and all other relevant regulatory guidelines.

All electronic data will be stripped of identifiers and stored in password-protected files on servers at the University of Miami Center on Aging. These data are password secured for minimal access to authorized personnel associated with the study. For each data file, a code number will be assigned, and the master list, linking code numbers with names, will be stored separately. At the conclusion of the project, the record linking the assigned research number and participant identity will be destroyed. Data will be entered into password secured databases by staff authorized by the principal investigator to do this, and they will abide by confidentiality regulations of the HSRO. No subject will be identified by any published report.

11) Provisions to Monitor the Data to Ensure the Safety of Subjects*

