Identifying Events: As noted, we will operationalize adverse/safety events for the study and protocols for their resolution. All interventionists and assessors will be trained on these protocols. Initially we will base these protocols on those developed for the HOLA pilot trial. For that trial, there were two categories of events: adverse events and safety alerts. These events may be identified during the baseline interview or the intervention period. Baseline adverse events are items that are identified and recorded by the interviewer during the baseline interview and are unrelated to the study or intervention. Adverse events are situations that occurred during the intervention period and are identified by the interventionist or by the interviewer during the 3 month assessments or any off-protocol interaction with a participant. All off-protocol contacts will be recorded. Adverse events occur anytime following randomization until study completion. Safety alerts are identified by the interviewer during the baseline interview or occur anytime following randomization until study completion. Below are the specific events that trigger a formal response:

Acute Baseline Alerts/Adverse Events

- Hospitalization of Participant
- Institutionalization of Participant
- Emergency Room Visit of Participant
- Death of Participant

Safety Alerts/Adverse Events

- Severe Medical Problem of Participant
- Participant has CES-D score greater than or equal to 20
- Participant Abuse
- Participant threatens to harm him or herself or others

The baseline adverse events and adverse events that occur during the study period are events that fall within the standard definition of adverse events within a clinical intervention study. Safety alerts are those events that do not fall within the standard definition of adverse events but are specific to the participant population.

Reviewing and Reporting Adverse Events: When an alert or adverse event is

IRB Study Number: 20181032

Version 8, Date: 07/16/2021

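### With all 18 men receiving HOLA and no comparator, the planned moderator test can identify predictors of change but not moderators of a HOLA effect

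*Combined protocol and SAP*

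**What the plan says.** The relevant statements in the combined protocol and SAP are these.

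- Section 6 (Number of Subjects): "18 older Latinos age 50+ will be enrolled".
- Section 8 (Procedures Involved): "After the baseline assessment, participants will be enrolled into the HOLA intervention". No other destination for participants is named.
- Section 3 (Objectives), Aim 3: the stated goal is to explore changes in risk factors, psychosocial functioning and quality of life among men enrolled in HOLA.
- Section 10 (Data Management): outcomes are analysed by one-way and repeated-measures ANOVA over time, with no group factor. The repeated-measures model is said to be one that "is appropriate to explore the intervention effects on cardiometabolic risk factors".
- Section 10, on covariates: "In the exploratory analyses, we will use age, SES, and years of education as covariates". If medications are changed or started, "then we will adjust for them in them in the exploratory analysis as well". The paragraph ends: "Covariates will be tested as moderators of treatment response".

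A randomized controlled trial is mentioned as a design only for the larger study that would follow (Aim 2).

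**The concern.** A moderator of a treatment changes the difference between treatment and no treatment. Testing for one needs both conditions, or some other source of information about what would have happened untreated. This plan has only the treated condition.

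Older, poorer or less educated men may change differently over 4 to 7 months for reasons unrelated to HOLA, such as natural course, regression to the mean or other care. A covariate-by-visit association cannot tell these apart from a HOLA effect that differs between men. Adjusting for medication changes, as Section 10 proposes, deals with one of these sources and only in part.

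What is at stake is the label on the result. As written, a positive test would be called moderation of treatment response when it may only show which men would have changed anyway. A null test would not exclude moderation either, because the two parts can cancel.

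**Working it through.** The plan states no power, alpha or effect size for this test, so there is no figure to reproduce. The check is whether the moderator effect can be estimated at all.

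**1. Model.** Let X be a covariate and T = 1 for HOLA, 0 for no HOLA:

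change = c + d·T + a·X + b·X·T + error

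Here a is the covariate's link with change in the absence of HOLA, and b is moderation of the HOLA effect.

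**2. Insert the design.** Sections 6 and 8 put all 18 men on HOLA, so T = 1 throughout. The T column then equals the intercept and the X·T column equals X:

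change = (c + d) + (a + b)·X + error

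The design matrix [1, X, T, X·T] has rank 2 of 4. Only a + b can be estimated. The number of men does not enter this result, so a larger single-arm study has the same problem.

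**3. Numerical confirmation.** Assumptions: 18 men, X and residual SD of 1, d = −0.3, two-sided 5% test, 10,000 runs per row.

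| a | b | Mean slope, single arm | Share positive |
|---|---|---|---|
| 0.5 | 0 | 0.50 | 48% |
| 0 | 0.5 | 0.50 | 48% |
| 0.25 | 0.25 | 0.50 | 49% |
| 0.5 | −0.5 | 0.00 | 4.9% |

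Pure prediction, pure moderation and a mixture give the same answer. In the last row real moderation is present and the test does not see it.

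For contrast only, a hypothetical split of 9 and 9 men gives rank 4 of 4. The interaction estimate then averages 0.00 when b = 0 and 0.50 when b = 0.5, although power for b = 0.5 is only about 14%. A comparator makes b estimable; at this size it would not make it precise.

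**4. Illustration of one non-HOLA source.** Every input here is an assumption, because the documents give no reliability or correlation, and the entry criterion on cardiometabolic risk in Section 5 gives no cut-off. Suppose HOLA has no effect and men enter from the top half or top quarter of the baseline value. Let measurement reliability be 0.5 to 0.85, and let the covariate correlate with the true outcome level. With 18 men and a 5% test:

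- correlation 0.3 to 0.7: about 5%–15% of studies positive;
- correlation 0.3 or less: about 5%–7%;
- no selection on baseline: about 5%, the nominal rate.

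The conclusion from step 2 needs none of these values.

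**The case against.** The strongest reply is that this is mainly wording. Treatment response can be read loosely as pre-post change among treated men. Aim 3 speaks only of exploring changes, and Section 10 uses ANOVA to illustrate change in scores. On that reading the analysis is a predictor analysis under a loose name, and relabelling it alters no number. This stands in part: the text is ambiguous. However, the same section says its repeated-measures model "is appropriate to explore the intervention effects on cardiometabolic risk factors", which supports a causal reading, and a predictor analysis should be called one.

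The second reply is that the consequence is small. The study is declared unpowered for hypothesis testing, the covariate work is exploratory, and the feasibility criteria do not use it. The stated source for design modifications under Aim 2 is the project evaluation questionnaire. All of this stands and limits the severity. It does not answer the identification problem, because those labels concern precision.

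A reader might also infer more than the documents support:

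- *That false moderators are likely.* Nothing in the documents supports strong correlations of age, SES or education with the outcomes. At modest ones the illustration stays close to 5%.
- *That there is a second arm.* Section 10 says "Adequate retention will be defined as 85% or more of randomized subjects completing the post-intervention assessment" and Section 11 says "Adverse events occur anytime following randomization until study completion", but no arms, ratio or procedure accompany these words. Section 11 initially bases its event protocols on the HOLA pilot trial, so its wording may be carried over. This is a separate consistency point and adds no weight here.
- *That medication changes will be tested as moderators.* Section 10 names age, SES and education as covariates and says medications will be adjusted for. Its last sentence does not exclude medications, but does not name them either.
- *That a positive test would misdirect the later trial.* The documents do not say how such a result would be reported or used.

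**Conclusion.** The concern holds as a minor point. Section 10 announces a test of moderation that the single-arm design cannot deliver at any sample size; what can be estimated is the covariate's total association with change. This rests only on all participants receiving HOLA and on the absence of any comparator, both of which follow from the text. It does not affect the primary feasibility aim, and no decision rule depends on it. The size of any misleading result cannot be derived from the documents, and the percentages above are assumption-based illustration only.

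**What to change.** In Section 10, replace the sentence on moderators with wording such as:

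*Age, SES and years of education will be described as exploratory predictors of change from baseline (slope with 95% CI), not as moderators of treatment effect; medication changes, which arise after baseline, will be used only for adjustment or sensitivity analysis.*

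In the repeated-measures ANOVA rationale in the same section, replace the reference to exploring intervention effects with one to exploring changes, to match Aim 3. Leave moderation to the later randomized trial.

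Separately, reconcile the randomization wording in Sections 10 and 11 with the single-arm description in Section 8.

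The cost is one sentence, one phrase and a consistency edit, with no new data, visits or models. What is given up is a claim that the design cannot support.

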In addition, we will also collaborate with another study, the Clinic Registry Project (IRB#20160911), which serves as a consent to contact database, to contact eligible participants. They will provide us with contact information for participants in their study who have consented to be contacted by other studies. When contacting participants, the CHW will follow the phone script for calling UHealth consent to contact participants that has been tailored to this study.

8) **Procedures Involved***

Participants will be assessed at three time points (before starting the study, 4, and 7 months after the first interview) on measures of cardiometabolic risk factors (waist circumference, dyslipidemia, hypertension, and glucose), psychosocial functioning, and health-related quality of life.

All participants will read and sign an informed consent document and a HIPAA Research Authorization – Form B approved by the University of Miami Institutional Review Board (IRB). They will initially be provided with a verbal summary of the study and for those who appear to have problems reading the consent form it will be read aloud. Participant payments will be graduated. Participants will receive \$15 on the first visit, \$25 on the second visit, and \$35 on the third visit (total of honoraria = \$75).

Prior to starting the baseline assessments, blood draws will take place at the UM/JMMC Adult HIV Outpatient Clinic. Study staff will obtain initial HDL-C, LDL-C, triglycerides, insulin, and HbA1c levels via review of the electronic medical records. Trained and certified research assistants (RAs) who have at least a bachelor's degree will conduct all assessments in private offices at the UM/JMMC Adult Outpatient HIV Clinic, at a private interview room at the CTRS located on the 7th floor of the Don Soffer Clinical Research Center, or the participant's home. To ensure privacy in the home, we will conduct the interview in a private room with a door of the participant's choosing away from any common areas. In the event that there are other people in the house, the door can be closed to maintain privacy. In the event that an in-person interview is not feasible then the interview will be

IRB Study Number: 20181032

Version 8, Date: 07/16/2021

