conducted over the telephone. At 4 and 7 months after the initial interview, fasting blood samples will be drawn via venipuncture and stored at 4°C until analysis. HOMA will be calculated, providing a measure of insulin resistance. Study measures will be administered after the blood draws.

Assessment Measures

Cardiometabolic Risk: list of current medications, waist circumference, total cholesterol, HDL-C, LDL-C, triglycerides, blood pressure, and HbA1c, will be used to measure cardiometabolic risk.

Dementia Screen: The Mini Mental Status Exam (MMSE) will be used to screen for dementia. A Mungas-adjusted score of 23 or below indicates cognitive impairment.

Walking Ability: The 10 meter walk test will be used to evaluate walking ability, which has been used as a screening instrument to measure functional mobility and gait speed in physical activity interventions with older adults.

Demographics: The CLaRO Demographics Form will be used to collect demographic information (e.g., gender, education, income, preferred language, country of origin, time in the US, etc.) and will include a list of all diagnosed medical conditions and medications.

Acculturation: The 24-item Bidimensional Acculturation Scale (BAS) will be used to measure acculturation.

Depression Severity: The 20-item Center for Epidemiologic Studies Depression (CES-D) Scale and the 9-item Patient Health Questionnaire (PHQ-9) will be used to measure depression severity.

Anxiety Severity: The 7-item Generalized Anxiety Disorder (GAD-7) scale and the 14-item Perceived Stress Scale will be used to measure anxiety severity.

Social Support: Perceived social support will be measured using the 12-item Multidimensional Scale of Perceived Social Support (MSPSS).

Health Related Quality of Life: The SF-12 will be used to assess for health related quality of life.

Physical Activity: The 16-item Global Physical Activity Questionnaire (GPAQ) will be used to measure physical activity.

Stigma: The HIV Stigma Scale (HSS) is a 40 item measure of stigma and psychosocial aspects of having HIV.

IRB Study Number: 20181032

Version 8, Date: 07/16/2021

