Protection of Risks During Venipuncture: Blood draws will be performed by certified phlebotomists who routinely perform venipuncture; steps will be taken to diminish the risk of minimal discomfort, bruising, excessive bleeding, clotting, and/or fainting. If subjects have unusual symptoms,

IRB Study Number: 20181032

Version 8, Date: 07/16/2021

pain, or any other problems arising due to venipuncture, they can also contact the CHW or PI directly.

14) Potential Benefits to Subjects*

The potential benefits of the project to the participant is that the participant may acquire and practice health behaviors that lead to a decreased risk of developing cardiometabolic disease. The benefit to society is that the project may help demonstrate the effectiveness of the HOLA health promotion intervention in preventing cardiometabolic disease in HIV-infected patients.

In relation to the anticipated benefits, the risks to the subjects are reasonable in relation to the benefit of not developing a life-threatening cardiometabolic disease. Participants are de-identified to minimize loss of confidentiality; suicidality or severe depressed can be addressed by trained mental health professionals; discomfort during venipuncture is mitigated by trained phlebotomists.

15) Vulnerable Populations*

N/A

16) Multi-Site Research*

This is not a multi-site study.

17) Community-Based Participatory Research*

N/A

18) Sharing of Results with Subjects*

Study results will be published in scientific journals. Individual subject results will not be shared unless the safety of the participant is at risk.

19) Setting

Group walks will be conducted at a public park that is centrally located to the participants. All assessments and blood draws will be conducted in private rooms at the at the UM/JMMC Adult HIV Outpatient Clinic.

20) Resources Available

Department of Psychiatry and Behavioral Sciences

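### The protocol contradicts itself on where assessments take place, and nothing holds, records or adjusts for each man's setting when blood pressure and waist are compared across visits.

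*Combined protocol and SAP*

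**What the plan says.** Section 19 (Setting) allows one location: "All assessments and blood draws will be conducted in private rooms at the at the UM/JMMC Adult HIV Outpatient Clinic".

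Section 8 (Procedures Involved) allows more. Research assistants "will conduct all assessments in private offices at the UM/JMMC Adult Outpatient HIV Clinic", in an interview room at the research centre "located on the 7th floor of the Don Soffer Clinical Research Center, or the participant's home". For home visits it adds: "To ensure privacy in the home, we will conduct the interview in a private room with a door". It also has a fallback: "In the event that an in-person interview is not feasible then the interview will be" done by telephone.

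The list of assessment measures in section 8 opens with cardiometabolic risk: "list of current medications, waist circumference, total cholesterol, HDL-C, LDL-C, triglycerides, blood pressure, and HbA1c, will be used to measure cardiometabolic risk". On sequence, section 8 says: "Study measures will be administered after the blood draws". It takes the initial lipid, insulin and HbA1c values from the medical record. Blood pressure and waist are not among the values taken that way.

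The visits are at baseline, 4 months and 7 months. After the baseline assessment, participants go into HOLA. Section 10 (Data Management) uses the word randomized in its retention criterion, but section 8 describes no allocation and no comparator. Section 10 analyses change over time by ANOVA, with age, SES and years of education as covariates and an adjustment for changes in medication.

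**The concern.** The two location statements both cover all assessments, so they cannot both be followed. Staff who use the home option in section 8 depart from section 19.

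The statistical interest is in the measures taken by hand. Aim 3 looks at change within each man in a set of risk factors that includes hypertension and waist circumference. There is no second arm in which a shift in measuring conditions would also appear and cancel. If some men are measured in the clinic at one visit and at home at another, any systematic difference between those settings goes into the estimated change. Since the setting is neither fixed nor recorded, it could not be identified or removed afterwards.

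The telephone fallback leaves a related gap. Staff cannot take blood pressure or waist by telephone, and the protocol does not say what happens to those two measures when it is used.

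**Working it through.** **Step 1: set the sections side by side.**

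| Point | Section 8 | Section 19 |
|---|---|---|
| Scope | All assessments | All assessments and blood draws |
| Permitted places | HIV clinic, research-centre room, home | HIV clinic only |
| Telephone | Allowed for the interview | Not mentioned |
| Baseline blood draw | HIV clinic | HIV clinic |
| 4- and 7-month draws | Place not stated | HIV clinic |

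**Step 2: see whether blood pressure and waist fall within the scope.** Section 8 does not name them in the sentence on location. They come in through two links: that sentence covers all assessments, and both are listed as assessment measures. Neither is on the list of baseline values taken from the medical record. On the text, the home option therefore extends to them, although this is an inference.

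**Step 3: look for a safeguard.** I found no rule for one setting per participant, no instruction to record the setting, no description of how blood pressure is measured, and no setting term among the covariates in section 10.

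**Step 4: illustrate the size.** The plan has no figure to reproduce: it states N = 18 without a calculation and gives no standard deviation or effect size.

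Inputs:
- n = 18 (section 6).
- d = mean systolic difference between clinic and home. Assumed: 3, 5 or 10 mmHg.
- k = net number of men who switch, that is, those moving one way minus those moving the other. Assumed: 0, 3, 6 or 9.

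Formula: spurious mean change = k × d / 18.

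| k | d = 3 | d = 5 | d = 10 |
|---|---|---|---|
| 0 | 0 | 0 | 0 |
| 3 | 0.5 | 0.8 | 1.7 |
| 6 | 1.0 | 1.7 | 3.3 |
| 9 | 1.5 | 2.5 | 5.0 |

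For example, 6 × 5 / 18 = 1.7 mmHg and 9 × 10 / 18 = 5.0 mmHg. The sign depends on the direction of the net switch. If every man keeps one setting, k = 0 and the shift is zero.

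The sum assumes that all 18 men have both readings and that d is the same for each of them. It treats the research-centre room as equivalent to the clinic. I have not done the same for waist, which should depend less on setting.

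**The case against.** The strongest reply is that the home option was meant for questionnaires only. Both the privacy sentence and the telephone sentence in section 8 speak of an interview, and study measures follow the blood draws, which section 19 places in the clinic. That is a natural reading and may be what was intended. But the sentence granting the home option covers all assessments, and nothing excludes the physical measures. If questionnaires were meant, saying so settles this part.

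A second reply is that every number in the illustration beyond n = 18 is assumed, and that the same trained and certified assistants measure in every setting. That stands: the documents do not show that any man will switch. It bears on the size of the effect, not on the contradiction or the missing safeguard.

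A third reply is that Aim 3 is secondary and exploratory, the study is not powered to test a hypothesis, and none of the section 10 success criteria (recruitment, refusal, retention, attendance) uses blood pressure. That also stands, and it sets the severity.

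Two stronger readings are tempting, and neither is supported:

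- **The shift would flatter HOLA.** A reader might assume that men move from clinic to home and read lower there. The documents give neither the direction of switching nor the difference between settings. Switches the other way reverse the sign, and balanced switching gives zero.
- **The 10 m walk is affected too.** A reader might infer a between-visit shift, or that a man could be excluded because his home lacks space. The protocol describes the walk as a screen ("The 10 meter walk test will be used to evaluate walking ability, which has been used as a screening instrument") and section 13 treats it as a one-time indicator, so it has no between-visit change to distort. The exclusion is for being unable to complete the test, which a short room does not show. The private-room wording for homes concerns the interview.

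**Conclusion.** The point holds as a minor one. Sections 8 and 19 contradict each other in the current text, and the plan neither fixes, records nor adjusts for the setting of blood pressure and waist. In this single-arm design, a change of setting would be confounded with a change over time.

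The effect is possible, not demonstrated. The illustrated 0 to 5.0 mmHg, in either direction, rests entirely on the assumed 3 to 10 mmHg difference and the assumed net switch of 0 to 9 men. The primary feasibility criteria do not depend on blood pressure. The contradiction does touch Aim 1, which includes the feasibility of the assessment procedures, and Aim 2, which is to inform a confirmatory trial. Both are better served by a defined measurement setting.

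**What to change.** 1. Reconcile sections 8 and 19 so that they name the same permitted places for the same activities, including the place of the 4- and 7-month blood draws.
2. State that blood pressure and waist are taken in the same setting at every visit for each man, by default the clinic attendance at which blood is drawn. Limit home and telephone contacts to questionnaires.
3. Record the setting of the physical measures at each visit.
4. Report the exploratory blood-pressure change with all men, and again without any man whose setting changed. With only 18 men, showing both is preferable to removing anyone from the main summary.

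The cost is protocol wording, one extra field on the data form and one extra line in the results. Whether any attendance is added depends on step 1, because only section 19 places the later draws in the clinic, and no section says that the draw and the assessment share one attendance. The small downside is that a man who cannot come to the clinic may lack a comparable blood-pressure or waist value.
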